# **PROTOCOL HISTORY**

Document	Amendment Type	Date
Amendment 3.0	Global	26 April 2022
Amendment 2.0	Global	19 October 2021
Amendment 1.3	Country-specific (Greece)	06 October 2021
Amendment 1.2	Country-specific (Serbia)	23 July 2021
Amendment 1.1	Country-specific (Germany)	14 July 2021
Amendment 1.0	Global	09 March 2021
Original Protocol	Not applicable	16 December 2020

# **PROTOCOL SYNOPSIS**

**Sponsor:** Arena Pharmaceuticals, Inc.

#### Name of investigational study drug: APD418

**Protocol title:** A Phase 2, Multicenter, Randomized, Double-Blind, Placebo-Controlled Study to Assess the Hemodynamic Effects, Safety, Tolerability, and Pharmacokinetics of APD418 in Subjects with Heart Failure with Reduced Ejection Fraction

Protocol number: APD418-201

Phase: 2

Country(ies)/region(s) (planned): United States and Europe

#### **Objectives:**

Primary Objective

• To assess the effect of intravenous (IV) infusion of APD418 on hemodynamic status based on cardiac index (CI) in subjects with heart failure with reduced ejection fraction (HFrEF)

Secondary Objectives

- To assess the effect of IV infusion of APD418 on additional hemodynamic, vital sign, and systolic function parameters in subjects with HFrEF
- To assess the pharmacokinetics (PK) of IV infusion of APD418 in subjects with HFrEF
- To assess the safety and tolerability of IV infusion of APD418 in subjects with HFrEF

## Exploratory Objectives

- To assess select exposure-response (PK/pharmacodynamic [PD]) relationships in subjects with HFrEF
- To assess the relationships between select subject/disease characteristics and select PD measures in subjects with HFrEF
- To assess the effect of IV infusion of APD418 on markers of renal function in subjects with HFrEF
- To assess the effect of IV infusion of APD418 on cardiac biomarkers in subjects with HFrEF
- To assess the effect of IV infusion of APD418 on additional systolic and diastolic function parameters in subjects with HFrEF
- To assess the effect of IV infusion of APD418 on urine output in subjects with HFrEF
- To assess the effect of IV infusion of APD418 on body weight in subjects with HFrEF
- To assess the OATP genotype

#### Study Design:

This is a Phase 2, multicenter, randomized, double-blind, placebo-controlled, single-dose study assessing the hemodynamic effects, safety, tolerability, and PK of APD418 in subjects with HFrEF to be conducted in 2 parts. Each part consists of a Screening Period (up to 21 days for Part A and up to

14 days for Part B), a single dose of randomized study treatment (APD418 or placebo) as a 6-hour IV infusion on Day 1 (Dosing Period) followed by an 18- to 24-hour in-clinic observation period (Postdose Period), and a Follow-Up phone call 7 days (± 2 days) after discharge. Subjects participating in Part A cannot participate in Part B.

On Day 1, potential eligible subjects (per initial Screening criteria) will undergo additional eligibility assessments during the Predose Period. Hemodynamic eligibility criteria based on right heart catheterization (RHC) will be assessed at Baseline for final confirmation of eligibility and randomization. Hemodynamic parameters based on RHC will be assessed at the end of Baseline (after at least a 2-hour stabilization period), during the Dosing Period throughout the study treatment administration (6-hour IV infusion), and for an additional 1 hour after cessation of study treatment administration. Subjects will continue to be observed during the Postdose Period for a minimum of 18 hours after the end of study treatment administration for PD, PK, and safety assessments prior to discharge on Day 2. Subjects will be contacted by phone call for follow-up 7 days (± 2 days) after discharge.

This study has an adaptive design, in which dose escalation in Part A will inform dose expansion in Part B. Part A is a single-ascending dose (SAD) study planned to consist of 5 cohorts. In each cohort, subjects will be randomized to APD418:placebo in a 5:2 ratio. Randomization will be stratified by Screening LVEF (> 25%,  $\leq 25\%$ ). Following completion of all planned cohorts in Part A, 2 APD418 doses studied in Part A will be selected for expansion in Part B. Part B is a parallel-treatment group study planned to consist of a placebo group and 2 APD418 treatment groups by randomizing additional subjects in 1:1:1 ratio (15 subjects are planned in the placebo group and each APD418 treatment group). Randomization will be stratified by Screening LVEF (> 25%,  $\leq 25\%$ ) and baseline carvedilol use (yes, no).

Each subject will receive a single dose of study treatment as an IV infusion over a duration of 6 hours. The initial APD418 dose to be studied in the first cohort of Part A will be 0.17 mg/kg/h (total dose 1 mg/kg). After 7 subjects have completed treatment in each cohort in Part A, an assessment of the safety/tolerability and PK data will be conducted by the dose escalation committee (blinded data review by the Sponsor and Investigator representatives) to determine whether dose escalation to the next dose level in Part A can occur. Doses for each subsequent cohort in Part A may be adjusted depending on the safety, tolerability, and PK results of previous cohort(s). The maximum dose in the study will not exceed 2 mg/kg/h (12 mg/kg) without a protocol amendment. At the conclusion of Part A, the dose selection committee will perform safety/tolerability and PD data assessment to identify 2 APD418 doses to be expanded in Part B (unblinded review of Part A data by the Sponsor representatives who are not directly involved in study conduct; site staff and sponsor representatives involved in study conduct will remain blinded throughout the study). Additional details about the dose escalation and the dose selection process are described in Sections 10.6.2 and 11.9. Additional subjects and/or cohorts may be enrolled in the study as described in Sections 6.4 and 11.9. The sample size will not increase by more than approximately 15% without a protocol amendment.

## Number of subjects (planned):

Approximately 80 subjects (25 placebo; 55 APD418) are planned to be enrolled in the study. In Part A, 5 cohorts are planned and 7 subjects are planned to be enrolled in each cohort (5 APD418:2 placebo per cohort; total N = 35). In Part B, 2 APD418 doses assessed in Part A will be expanded by enrolling 45 additional subjects (15 subjects are planned in the placebo group and each APD418 treatment group; total N = 45).

## **Eligibility criteria:**

## Inclusion criteria:

Subjects must meet all of the following key inclusion criteria to be eligible for enrollment into the study:

- Advanced chronic HFrEF, defined as left ventricular ejection fraction (LVEF) ≤ 35% at Screening, including documented history of HFrEF (LVEF ≤ 35%) for at least 4 months prior to Screening
- New York Heart Association (NYHA) Class II-IV
- $CI \le 2.5 \text{ L/min/m}^2$  and pulmonary capillary wedge pressure (PCWP)  $\ge 15 \text{ mm}$  Hg at Day 1
- Males and females 18 to 85 years of age inclusive, at time of informed consent
- Body mass index 18.0 to 37.0 kg/m^2, inclusive, and body weight < 150 kg at Screening and Day 1

Additional inclusion criteria are listed in Section 4.1.

## Exclusion criteria:

Subjects will be excluded from the study if they meet any of the following key exclusion criteria:

- Hemodynamically unstable at Day 1 or in the opinion of the Investigator likely to progress to becoming hemodynamically unstable during the course of the study
- Treated with inotropes such as dobutamine, dopamine, or milrinone within 72 hours of Day 1 or with levosimendan within 21 days of Day 1, or expected to require therapy with these drugs any time from Day 1 through the end of study conduct
- Treated with IV vasoactive therapy other than inotropic agents listed in Exclusion Criterion 2 or IV diuretic therapy within 24 hours of Day 1, or expected to require IV therapy any time from Day 1 through the end of the in-clinic observation Postdose Period
- Treated with carvedilol at a dose higher than total of 25 mg per day any time within 72 hours of Day 1 through the end of the in-clinic observation Postdose Period
- Use of any other therapy directly acting on the beta-3 adrenergic receptor (β3-AdrR; eg, mirabegron) any time within 14 days of Day 1 through the end of the in-clinic observation Postdose Period
- Use of a phosphodiesterase-5 (PDE5) inhibitor any time within 4 days of Day 1 through the end of the in-clinic observation Postdose Period
- Receiving any mechanical (respiratory or circulatory) or renal support therapy at Screening or Day 1
- Systolic blood pressure (SBP)  $\leq$  90 mm Hg or  $\geq$  160 mm Hg at Screening or Day 1
- Heart rate (HR) < 50 beats per minute (bpm) or > 110 bpm at Screening or Day 1
- Patients suffering from current infection or patients that have recovered from recent Coronavirus disease 2019 (COVID-19) infection that in the opinion of the Investigator would prevent the individual from participating in the study due to risk to the scientific validity of study assessments or to the patient's personal well-being

Additional exclusion criteria are listed in Section 4.2.

## Test product, dose, and mode of administration:

APD418, the investigational medicinal product, is an IV formulation containing active pharmaceutical ingredient (APD418) provided as 15 mg/mL (adjusted free-base concentration) strength. Diluted APD418 IV solution will be prepared for doses less than 1800 mg.

Subjects assigned to active treatment will receive a single dose as an IV infusion over a duration of 6 hours. The initial APD418 dose to be studied in the Cohort 1 of Part A will be 0.17 mg/kg/h (1 mg/kg). Planned doses for the remaining 4 cohorts in Part A are 0.50, 1.0, 1.5, and 2.0 mg/kg/h or 3, 6, 9, and 12 mg/kg, respectively. Doses for each subsequent cohort in Part A may be adjusted depending on the safety, tolerability, and PK results of previous cohort(s). The maximum dose in the

study will not exceed 2 mg/kg/h (12 mg/kg) without a protocol amendment. At the conclusion of Part A, 2 APD418 doses will be selected for expansion in Part B based on safety/tolerability and PD data. Additional details about the dose escalation and the dose selection process are described in Sections 10.6.2 and 11.9.

## **Duration of treatment:**

This is a single-dose study. Study treatment will be administered only on Day 1 of the study.

## Reference therapy, dose, and mode of administration

Placebo will be packaged to match APD418. Volume and mode of administration of placebo will match that of APD418 to maintain the blind.

## **Endpoints:**

Primary endpoint:

Change in CI measured by RHC from Baseline to end of IV infusion at 6 hours

Secondary endpoints:

- Change in the following hemodynamic parameters measured by RHC from Baseline to end of IV infusion at 6 hours:
  - Cardiac output (CO)
  - Pulmonary capillary wedge pressure (PCWP)
  - Right atrial pressure (RAP)
  - Systolic/diastolic pulmonary arterial pressure (PAS/PAD)
  - Pulmonary artery pulsatility index (PAPi)
  - Systemic vascular resistance/systemic vascular resistance index (SVR/SVRI)
  - Pulmonary vascular resistance (PVR)
- Change in the following vital sign parameters from Baseline to end of IV infusion at 6 hours:
  - Systolic blood pressure (SBP)
  - Diastolic blood pressure (DBP)
  - Mean arterial pressure (MAP)
  - Heart rate (HR)
- Change in the following hemodynamic and systolic function parameters measured by echocardiogram (ECHO) from Baseline to end of IV infusion at 6 hours:
  - Stroke volume (SV)
  - SV index (SVI)
  - Left ventricular ejection fraction (LVEF)
  - Fractional shortening (FS)
  - Left ventricular end systolic/left ventricular end-diastolic volume (LVESV/LVEDV) and diameter
  - Left ventricular global longitudinal strain (LVGLS)
  - Left ventricular circumferential strain (LVGCS)
- Change in hemodynamic (measured by RHC) and vital sign parameters listed above at intermediate timepoints during 6-hour IV infusion (during Dosing Period)
- Plasma and urine PK parameters of APD418

• Safety and tolerability of APD418 by incidence of all treatment-emergent adverse events (TEAEs)

Exploratory endpoints:

- Change in hemodynamic parameters (measured by RHC) listed above at 1 hour after end of 6-hour IV infusion (during Postdose Period)
- Change in vital sign, hemodynamic (measured by ECHO), and cardiac systolic function (measured by ECHO) parameters listed above for 18 hours after end of 6-hour IV infusion (during Postdose Period)
- The relationships between select APD418 plasma exposure measures and change in select PD parameters
- The relationships between select subject/disease characteristics (eg, Baseline LVEF, Baseline CI, Baseline SBP, duration of HFrEF, renal function, concomitant medications) and change in select PD parameters
- Change in markers of renal function (estimated glomerular filtration rate [eGFR], blood urea nitrogren [BUN], cystatin C, urine protein/creatinine ratio, urinary sodium excretion)
- Change in cardiac biomarkers (N-terminal pro b-type natriuretic peptide [NT-pro-BNP, high-sensitivity cardiac troponin T [hs-cTnT])
- Change in the following additional systolic and diastolic function parameters measured by ECHO: E, A, E', S', early/late diastolic velocities [E/A] ratio, early mitral filling velocity/early diastolic mitral annular velocity [E/E'] ratio), tricuspid annular plane systolic excursion (TAPSE), tricuspid regurgitation (TR) velocity, and left atrial (LA) volume index
- Change in urine output
- Change in body weight
- The genotype of OATP

## Safety Assessments:

Safety assessments will include adverse events (AEs), vital signs, clinical laboratory findings (including hs-cTnT), electrocardiograms (ECGs), physical examinations, and concomitant medications.

## Pharmacodynamic Assessments:

Assessments of PD will include change in hemodynamic, vital sign, and cardiac function parameters obtained from RHC and ECHO, cardiac biomarkers (NT-pro-BNP and hs-cTnT), markers of renal function (eGFR, BUN, cystatin C, urine protein/creatinine ratio, and urinary sodium excretion), as well as urine output and body weight. Potential relationship between select subject/disease characteristics (eg, Baseline LVEF, Baseline CI, Baseline SBP, duration of HFrEF, renal function, concomitant medications), and select PD measures (eg, change in CI) may be explored.

## Pharmacokinetic Assessments:

Blood samples for plasma PK analysis of APD418 will be collected at the following timepoints in relation to the start of the IV infusion: Baseline (within 2 hours prior to study treatment administration), during the Dosing Period at 0.5, 1, 2, 3, 4, 5, and 6 hours (within 10 minutes before the end of the IV infusion), and during the Postdose Period at 6.083, 6.167, 6.25, 6.5, 7, 8, 10, 18, and 24 hours.

Urine samples will be collected during the following intervals in relation to the start of the IV infusion: Baseline (within 2 hours prior to study treatment administration), 0 to 6 hours, 6 to 10 hours, and 10 to 24 hours.

## Statistical methods:

Determination of sample size:

Approximately 80 subjects are planned to be enrolled in this study (35 in Part A, 45 in Part B).

It is assumed that baseline CI, as measured with RHC, is normally distributed with a mean of 2.0 and a standard deviation (SD) of 0.5. Sixty-five evaluable subjects (20 subjects in each of the 2 APD418 treatment groups and 25 in placebo) is sufficient to achieve at least 80% power to detect a treatment effect of 0.45 in favor of APD418 (a clinically significant improvement of 22.5% from placebo) between each of the APD418 treatment groups and placebo by a 2-sample t-test using a 2-sided significance level of 0.05.

The primary analysis will be based on pooled data from subjects in Part A and Part B. There will be 2 APD418 treatment groups of 20 subjects each (planned to consist of 5 subjects from Part A and 15 subjects from Part B) and 1 placebo treatment group of 25 subjects (planned to consist of 10 subjects from Part A and 15 subjects from Part B).

A blinded review of the data to evaluate the assumption regarding the SD of the change in CI may be conducted. The planned sample size will not be reduced as a result of the sample size re-estimation. Details will be specified in the Statistical Analysis Plan (SAP).

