# **11.2.** Determination of Sample Size

Approximately 80 subjects are planned to be enrolled in this study (35 in Part A and 45 in Part B). It is assumed that CI, as measured with RHC, from Baseline to end of infusion is normally distributed with a mean of 2.0 and SD of 0.5. Sixty-five evaluable subjects (20 subjects in each of the 2 APD418 treatment groups and 25 in placebo) is sufficient to achieve at least 80% power to detect a treatment effect of 0.45 in favor of APD418 (a clinically significant improvement of 22.5% from placebo) between each of the APD418 treatment groups and placebo by a 2-sample t-test using a 2-sided significance level of 0.05.

The primary endpoint analysis will be based on pooled data from subjects in Part A and Part B. There will be 2 APD418 treatment groups of 20 subjects each (planned to consist of 5 subjects from Part A and 15 subjects from Part B) and one placebo treatment group of 25 subjects (planned to consist of 10 subjects from Part A and 15 subjects from Part B).

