## **11.7. Testing Strategy**

No formal testing strategy or adjustments of the Type I error will be employed for secondary or exploratory endpoints. Estimates and confidence intervals for treatment groups and from pairwise comparisons will be used in an exploratory manner.

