## **11.9. Dose Escalation and Dose Selection**

After treatment of each cohort in Part A, an assessment of the safety/tolerability and PK data will be performed by the dose escalation committee (blinded data review by the Sponsor and Investigator representatives) prior to dose escalation to the next dose level in Part A. The decision to escalate to the next planned dose level in Part A will be made with consideration of

the safety-related dose escalation stopping criteria and overall safety (including AEs, clinical laboratory, and vital sign/ECG data) and PK data of each cohort, as described in Section 10.6.2.

Doses for each subsequent cohort in Part A may be adjusted depending on the safety, tolerability, and PK results of previous cohort(s). The maximum dose in the study will not exceed 2 mg/kg/h (12 mg/kg) and will not produce exposures to APD418 higher than that predicted for a 12 mg/kg dose (ie,  $C_{max}$  of 5700 ng/mL or AUC0- $\infty$  of 39,000 ng·h/mL) without a protocol amendment.

The dose escalation committee may decide to evaluate an alternative dose(s) in the subsequent cohort(s) in Part A in the following scenarios:

- Based on the safety profile observed, lower or higher than planned dose(s) may be chosen to be evaluated in the subsequent cohort(s) (not to exceed 12 mg/kg without a protocol amendment)
- If large deviations from the expected PK profile are observed, adjustment to the planned dose escalations may occur to ensure evaluation of dose levels that will elicit appropriate exposure
- If warranted based on the emerging safety and PK data, up to 1 additional or 1 fewer cohort may be studied than originally planned

At the conclusion of Part A, the dose selection committee will perform a safety/tolerability and PD data assessment to identify 2 doses to be expanded in Part B (unblinded review of Part A data by the Sponsor representatives who are not directly involved in study conduct; site staff, and sponsor representatives involved in study conduct will remain blinded throughout the study). Selection of doses will be based on the criteria including, but not limited to:

- Doses selected for expansion in Part B have shown a favorable safety profile in Part A as determined by the criteria described in Section 10.6.2
- Doses selected for expansion in Part B have shown clinically relevant PD effects indicating a clinically meaningful benefit in cardiac function (eg, SV, CO, LVEF)

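### Part A subjects help choose the Part B doses and are then pooled into the primary comparison, with no selection-free estimate planned beside it

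*Combined protocol and SAP*

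**What the plan says.** Section 11.9 has a dose selection committee review unblinded Part A data and name two doses for Part B. It introduces the criteria with "Selection of doses will be based on the criteria including, but not limited to". One is a favourable safety profile; the other is that the doses "have shown clinically relevant PD effects indicating a clinically meaningful benefit in cardiac function (eg, SV, CO, LVEF"). No ranking rule is given. Five cohorts are planned, but "up to 1 additional or 1 fewer cohort may be studied than originally planned", so four to six doses may be candidates.

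The synopsis (Determination of sample size) states that "The primary analysis will be based on pooled data from subjects in Part A and Part B". Section 11.2 repeats this and gives the make-up of each 20-subject APD418 group: "planned to consist of 5 subjects from Part A and 15 subjects from Part B". Placebo is 10 subjects from Part A plus 15 from Part B.

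The primary model in Section 11.10 has treatment, timepoint, their interaction, stratification and Baseline CI. It has no term for study part. The protocol describes neither a Part B-only estimate nor a selection-adjusted one, and gives no caveat on the pooled result. Section 11.1 defers detail to the SAP. According to the biostatistics Note to File the SAP reached draft v0.4; its text is not in the documents.

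Section 8.4 ends the study before Part B if no dose shows a favourable safety profile and/or meaningful PD effects. It gives no threshold.

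**The concern.** A dose chosen because its five Part A subjects did well carries some of their good luck with it. Pooling those subjects with the Part B subjects moves part of that luck into the primary estimate, while the analysis treats the dose as if it had been fixed in advance. Cardiac output makes the link close: it and the primary endpoint come from the same thermodilution readings and differ only by body size.

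What is at stake is mainly the point estimate. Section 3.2 says the study is meant to inform the design and dose selection of later studies. An effect overstated by selection would make those studies too small, and the bias does not vanish when the drug works.

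**Working it through.** **Inputs.** From the synopsis, Section 11.2 and Section 11.9: five candidate doses (four to six allowed), 5 APD418 subjects per dose in Part A, 15 per arm in Part B, pooled groups of 20 and 25, effect 0.45, two-sided 0.05, SD 0.5. What the SD describes is unclear. The synopsis attaches it to baseline CI, while Section 11.2 says CI from Baseline to end of infusion is "normally distributed with a mean of 2.0 and SD of 0.5". I use 0.5 as the SD of change and vary it.

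**Assumptions not in the documents.** The two top-ranked doses are selected on a measure with subject-level correlation ρ to change in CI, with ρ from 0.3 to 1. True effects are equal across doses unless stated. The analysis is a two-sample t-test; the planned MMRM with Baseline CI would act through a smaller residual SD.

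**The plan's own figure.** SE = 0.5 × √(1/20 + 1/25) = 0.150. The noncentral t with 43 df gives 83.5% power at 0.45, which agrees with the stated minimum of 80%.

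**Bias without an early stop.** Only the active Part A mean is selected, and it carries weight 5/20:

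bias = (5/20) × E[order statistic of K standard normals] × SD/√5 × ρ

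For K = 5 the expected largest value is 1.163 and the second 0.495; SD/√5 = 0.5/2.236 = 0.2236.

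- Best dose, ρ = 1: 0.25 × 1.163 × 0.2236 = 0.065. At ρ = 0.5: 0.033. At ρ = 0.3: 0.0195.
- Second dose, ρ = 1: 0.25 × 0.495 × 0.2236 = 0.028. At ρ = 0.3: 0.008.
- Against the target effect: 0.0195/0.45 = 4% and 0.065/0.45 = 14%.
- At ρ = 0 the bias is zero.

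Simulation of the two-stage design (200,000 or more trials per scenario) agrees with these values.

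**Sensitivity of the best-dose bias (L/min/m²).**

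| Scenario | ρ = 0.3 | ρ = 1 |
|---|---|---|
| Five equal doses, SD 0.5 | 0.020 | 0.065 |
| SD 0.3 | 0.012 | 0.039 |
| SD 0.7 | 0.027 | 0.091 |
| Four doses | 0.017 | 0.058 |
| Six doses | 0.021 | 0.071 |
| True effects 0.09 to 0.45 | 0.017 | 0.054 |
| True effects 0 to 0.60 | 0.013 | 0.043 |

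Bias is proportional to ρ, so the 0.09 to 0.45 row should read about 0.3 × 0.054 = 0.016 at its low end; the simulated 0.017 differs by Monte Carlo error.

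**With the stop in Section 8.4.** The documents give no threshold. For illustration only, suppose Part B runs when the best Part A dose beats Part A placebo by more than 0.2 on the selection measure, and there is no true effect. Among trials that proceed, best-dose bias is about 0.033 (ρ = 0.3), 0.055 (ρ = 0.5) and 0.111 (ρ = 1). It is larger because the stop also favours trials with a low Part A placebo mean, and those subjects are 10 of the 25 pooled placebo subjects.

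**Part B alone.** Simulated bias is at most 0.001 in every scenario, with or without the stop. SE = 0.5 × √(2/15) = 0.183, and power at 0.45 is about 66%.

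**The case against.** The strongest case against runs as follows, and much of it stands.

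- **Selection may not follow PD rank.** Safety counts too and the criteria are left open. This stands: the bias is conditional.
- **Equal true effects are not what the plan expects.** Section 3.3 anticipates a low but detectable effect at the starting dose and possibly a maximal one at the top. This stands and lowers the bias, as the graded rows show.
- **The calculation without a stop ignores Section 8.4.** This stands, but it cuts both ways: the bias given that Part B runs is larger.
- **The 5/20 weight is not fixed.** Section 11.9 lets Part B change in size, Section 6.4 allows extra subjects, and Cohort 2 reached 15 in all. This stands, but a larger Part A share need not help. If, for illustration, each dose had 10 Part A subjects, 10 of 25 would give 0.40 × 1.163 × 0.5/√10 = 0.074 at ρ = 1.
- **The draft SAP may contain a Part B-only analysis.** It cannot be seen, so the statement about absence is limited to the protocol text.
- **The bias is small next to the noise.** At ρ of 0.3 to 0.5 it is at most 0.033/0.150 = 0.22 of the pooled SE, and simulated coverage of the pooled interval without a stop stays near 95% (0.939 to 0.950 for the best dose). This argues for a light remedy rather than none.

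A reader might also infer that the plan has a stated false-positive problem, or that the two dose comparisons need a multiplicity correction. The documents do not support that. The sample size is set "between each of the APD418 treatment groups and placebo by a 2-sample t-test using a 2-sided significance level of 0.05", with no familywise target. Section 11.7 says "No formal testing strategy or adjustments of the Type I error will be employed for secondary or exploratory endpoints" and then treats pairwise comparisons as exploratory, which partly answers how they are to be read in a Phase 2 study. With a stop of unstated threshold before Part B, no single error rate can be assigned to the plan.

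**Conclusion.** The point holds as a conditional one. The protocol uses the same Part A subjects to choose doses and to estimate their effect, and its text offers no estimate free of that selection.

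With five equally effective doses, SD of change 0.5, 5 of 20 subjects from Part A, no early stop and ρ from 0.3 to 1, the pooled best-dose estimate is too high by about 0.02 to 0.065 L/min/m², and the second dose by 0.008 to 0.028. Steeper true dose-response reduces the best-dose figure (to 0.013 to 0.043 in the steepest case tried). Conditioning on passing an assumed 0.2 gate with no true effect raises it to about 0.033 to 0.111. None of these ranges is the plan's own, because the selection rule, the stopping threshold and the correlation are not given.

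Two stronger readings go too far. Pooling need not be abandoned: it carries the planned power. Nor is any reported result shown to be biased: development stopped during Part A, and the Note to File limits the final safety and efficacy outputs to Cohorts 1 and 2. The point concerns the plan as written.

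**What to change.** Keep the pooled analysis as primary. In Section 11.10 and the SAP:

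1. Pre-specify, beside the pooled result, the Part B-only LS mean difference from placebo with its 95% confidence interval for each selected dose.
2. State that the pooled estimate and p-value are subject to selection because Part A subjects informed the choice of doses.

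The cost is one table and two sentences. The primary test loses no power, since no test is attached to the added estimate. At SD 0.5 the Part B-only estimate is less precise: its SE is 0.183 against 0.150 (0.183/0.150 = 1.22, so 22% larger), and 15 versus 15 has about 66% power against 83% for 20 versus 25. It is therefore a companion to the pooled estimate and not a replacement.
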